8.10.3 Exploratory Analyses

Exploratory analyses of biomarkers will examine their ability to predict clinical outcome. Analyses will be performed for OT, AVP, CORT, and BDNF. Changes in biomarker concentrations from pre-treatment levels will be used to analyze effects of acute dosing and to determine the time-course of elevated biomarker levels post-drug. Pre-treatment biomarker concentrations will be evaluated in regression analysis with condition assignment in Stage 1 and biomarker concentrations at baseline as predictors and treatment outcomes as dependent variables. Additionally, the effect of biomarker levels taken at the second experimental session, and two weeks and six months after the second experimental session, will be examined for correlation with LSAS outcomes.

Distributional characteristics will be examined for outliers and extreme values. If outliers are found in primary or secondary outcome measures, the sponsor will perform analyses with and without the outlying data.

Post-hoc exploratory analyses not identified in this SAP may be performed to further examine the study data. These analyses will be clearly identified as such in the final clinical study report.

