reliable indicator of elevated OT in the brain [41]. Findings of an association between elevated OT and detectable MDMA in peripheral blood were first reported in a naturalistic study of London nightclub attendees with and without detectable plasma MDMA levels [50]. Dumont and colleagues reproduced these results in humans and found that MDMA significantly elevated peripheral plasma OT levels in a placebo-controlled study in healthy volunteers [51], in addition to a positive association between elevated levels of OT and prosocial feelings. Hysek and colleagues replicated these results and further reported that administering a serotonin reuptake inhibitor, but not a norepinephrine uptake inhibitor nor several adrenergic antagonists, attenuated the effects of MDMA on OT levels, suggesting a serotonergic mechanism in producing elevated OT [52]. The effects of MDMA on OT could be partially responsible for changes in personality [53] and empathy [54]. However, the multi-level effects of MDMA on monoaminergic signaling and OT, combined with a therapeutic setting focused on enhancing functional skills, are more likely to provide the opportunity for a corrective emotional experience greater than OT alone, and could be useful in the treatment of social anxiety in autistic adults.

In addition to increased OT release, MDMA also results in increased secretion of the highly related neuropeptide AVP [50]. AVP neurobiology has been linked to social behavior in animal models and has been shown to increase social cognition when administered to healthy adult volunteers [46, 55, 56].

Also of interest is the stress-related hormone CORT, the major output of the hypothalamic-pituitary-adrenal (HPA) axis. MDMA has also been shown to increase CORT levels and it has been proposed that these changes are related to the stimulating effects of the drug [57]. In addition to the extensive prosocial behavioral effects of OT and AVP, their release has been shown to modulate other neuroendocrine systems, particularly the stress responsive activity of the HPA axis, that is dysregulated in individuals with social anxiety [58, 59].

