An overnight stay at a hotel located close to the site will be offered to subjects, accompanied by their support partners, if they live further than 30 miles from the site. Subjects will attend a 1-hour follow-up integrative therapy session on the day after the experimental session. Two additional integrative sessions will be conducted within the month following each experimental session, prior to outcome assessments being conducted one month after each experimental session. During integrative therapy sessions subjects will receive support in integrating their experiences and insights from the experimental session. The second experimental session will be scheduled approximately one month after the first experimental session, after outcome assessments have been completed.

All subjects, even those who have a prior diagnosis, will be clinically evaluated by the PI to determine autistic status. In addition, autistic status will be confirmed with the gold-standard diagnostic measure of autism and diagnosis of co-morbid psychological disorders will be conducted according to DSM-IV criteria at screening. Outcome measures will be assessed prior to treatment, during the treatment period, one month after each experimental session, and during the 6-month follow-up according to the Time and Events table. The sponsor will conduct an ongoing review of videos of therapy sessions, entry criteria, vital signs, and reaction data for completed sessions and any AEs. The sponsor will provide ongoing feedback to the co-therapist teams to ensure subject safety.

For all subjects blood samples will be obtained for biomarker analysis at baseline and during the study according to the Time and Events Table. Biomarker analyses including plasma OT, AVP, and CORT will be explored as surrogate endpoints at baseline, two hours after drug administration during the second experimental session, one month after the second experimental session, and at 6-month follow-up. Blood will be collected during the open-label extension Stage 2 two hours after drug administration during both

experimental sessions and one month after both experimental sessions. Biomarkers will be evaluated for predictive and prognostic power.

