Biomarkers will be evaluated for predictive and prognostic power. Separate estimates of effect size will be performed for OT, AVP and CORT. Changes in biomarker concentrations from pre-treatment levels will be used to analyze effects of acute dosing and to determine the time-course of elevated OT and AVP levels post-drug. Pre-treatment biomarker concentrations will be evaluated for predictive power using an exploratory hierarchical regression analysis with condition assignment in Stage 1 and biomarker concentrations at baseline as predictors and treatment outcomes as dependent variables. One regression will be performed with biomarker values taken at the second experimental session. A second regression will be performed on biomarker values taken two weeks after the second experimental session.

TAS-20 scores will be evaluated for predictive power using an exploratory hierarchical regression analysis with condition assignment in Stage 1 and TAS-20 scores at baseline as predictors and with LSAS scores as dependent measures. One regression will examine the predictive power of condition and baseline TAS-20 scores upon LSAS scores one month after the first experimental session and the other will investigate whether condition and baseline TAS-20 and will predict LSAS score at one month after the second experimental session.

Subjects who discontinue treatment prior to the second experimental session will be asked to complete the final outcome assessment prior to continuing to the 6-month follow-up whenever possible. The data from these subjects will be tested for equivalence to data from subjects completing the study per protocol. If found to be equivalent, data from these subjects will be combined for an exploratory intent-to-treat effect size estimate to examine results without bias towards subjects more likely to complete the study per protocol.

Stage 1 and Stage 2 outcomes in extension subjects will be compared after the outcome measure assessments are complete for all extension subjects.

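### SAP 8.10.3 names no arm term when relating post-dose biomarker levels to LSAS, so if MDMA moves both, the correlation can simply restate who received MDMA

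*SAP*

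**What the plan says.** SAP 8.10.3 sets out two biomarker analyses, one after the other. For pre-treatment concentrations it plans a "regression analysis with condition assignment in Stage 1 and biomarker concentrations at baseline as predictors and treatment outcomes as dependent variables". For later samples it continues that levels from the second session, and from "two weeks and six months after the second experimental session, will be examined for correlation with LSAS outcomes". The second sentence names no arm term, stratification, within-arm analysis or coefficient.

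Protocol 12.0 is worded differently. Directly after a hierarchical regression that has condition as a predictor, it adds: "One regression will be performed with biomarker values taken at the second experimental session" and "A second regression will be performed on biomarker values taken two weeks after the second experimental session". It does not say whether condition carries over into those two regressions.

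The stated aims go beyond description. Protocol 12.0 says: "Biomarkers will be evaluated for predictive and prognostic power". Protocol 4.0 says: "Biomarker analyses including plasma OT, AVP, and CORT will be explored as surrogate endpoints at baseline" and at later times. Protocol 2.3 adds insight into mechanism. On the expected drug effect, Protocol 2.2.3 reports a study that "found that MDMA significantly elevated peripheral plasma OT levels in a placebo-controlled study in healthy volunteers", and it also cites rises in vasopressin and cortisol.

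**The concern.** The arm term is named for the baseline samples, where randomisation should balance the arms on average. It is not named for the on-drug sample, where the arms are expected to differ. If treatment raises a biomarker and also lowers LSAS, the MDMA and placebo subjects form two separated clusters. A line through both clusters slopes downward even if, within each cluster, the biomarker says nothing about who improves.

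A surrogate or mechanistic reading needs an association beyond treatment assignment, and a pooled correlation cannot supply it. The artefact is most likely to appear when the drug works, which is when the result would be used to choose biomarkers for the next study. Several biomarkers and times are examined, and SAP 2.0 states that multiple comparisons are not corrected for.

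**Working it through.** The plan states no correlation, effect size or power for this analysis, so there is no figure to reproduce. The check asks what a pooled correlation shows when the within-arm correlation is exactly zero.

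**Inputs from the documents**
- Allocation: 8 MDMA and 4 placebo (SAP 2.0).
- Two-sided tests (SAP 8.0). Alpha of 0.05 is stated for the primary test in SAP 8.10.1 and is assumed here.
- On-drug sample: about two hours after dosing, second session (Protocol 5.2.3).

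**Assumed inputs**
- dB = rise in the biomarker on MDMA; dL = fall in LSAS on MDMA. Both are in within-arm SDs and normally distributed.

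**Expected pooled correlation.** With p = 8/12 and q = p(1 - p) = 2/9 = 0.222:

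r = -q·dB·dL / sqrt[(1 + q·dB²)(1 + q·dL²)]

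- dB = 2, dL = 1: -0.444 / sqrt(1.889 × 1.222) = -0.444 / 1.519 = -0.29.
- dB = 3, dL = 1.5: -1.000 / sqrt(3.000 × 1.500) = -1.000 / 2.121 = -0.47.

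**Rejection rates.** The critical |r| is t/sqrt(df + t²). This is 0.576 for the pooled correlation (10 df) and 0.602 for the correlation partialled on arm (9 df). Simulation with 200,000 trials per row gave:

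| dB | dL | expected r | pooled test rejects | arm-adjusted test rejects |
|---|---|---|---|---|
| 1 | 1 | -0.18 | 8.9% | 5.0% |
| 2 | 0 | 0 | 5.0% | 5.0% |
| 0 | 1.5 | 0 | 5.0% | 5.1% |
| 2 | 0.5 | -0.16 | 7.9% | 5.1% |
| 2 | 1 | -0.29 | 16.0% | 4.9% |
| 2 | 1.5 | -0.40 | 27.5% | 4.9% |
| 3 | 1 | -0.35 | 21.6% | 5.0% |
| 3 | 1.5 | -0.47 | 39.7% | 4.9% |

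A smaller run of 40,000 trials gave 39.1% in the last row. The two rows with a zero shift show that both shifts are needed: without either one, the pooled test holds its 5% level.

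**Price of adjusting.** For true within-arm correlations of size 0.3, 0.5 and 0.7, the arm-adjusted test has power of about 15%, 37% and 74%. Precision is correspondingly poor. For an observed partial r of 0.5, Fisher's z is 0.549 with standard error 1/sqrt(12 - 1 - 3) = 0.354. The 95% limits on that scale are -0.144 and 1.242, or about -0.14 and 0.85 for r.

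**Timing of the later samples.** The primary LSAS endpoint is visit 13, one month after session 2 (SAP 8.10.1). The post-session sample is placed at two weeks in SAP 8.10.3 and Protocol 12.0. Protocol 5.2.6 puts it at the second integrative session after session 2, which is visit 12 in Table 2. Protocol 4.0, SAP 4.0 and the Stage 1 Time and Events table put it at one month, which is visit 13. A visit 12 sample precedes the primary endpoint; a visit 13 sample coincides with it. The six-month sample follows it under every reading.

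**The case against.** The best defence is that the SAP is silent on arm and does not say that the arms are pooled. Protocol 12.0 can be read as keeping condition in its second-session and two-week regressions. The analysis is exploratory and leaves the primary LSAS test untouched. Even under the assumed shifts, about 60% to 84% of trials would show no significant pooled correlation. All of that stands. It limits the weight of the point but does not remove it, because an unqualified correlation, carried out as written, has no arm term, and the sentence before it shows that the authors knew how to include one.

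Four stronger readings are tempting, and the documents do not support them.
- *Any biomarker that MDMA raises will correlate with LSAS.* This also requires MDMA to change LSAS. Without that, the expected r is zero however large the biomarker shift.
- *All three samples are on-drug.* Only the second-session sample is. The later ones are affected only if the biomarker still differs between arms by then.
- *The post-session samples cannot predict outcome.* This is firm only for the six-month sample against visit 13. The other sample may precede visit 13, and even a visit 13 sample precedes the six-month LSAS.
- *The baseline regression must contain a biomarker-by-condition term because predictive power is claimed.* Without it the model speaks to prognosis, but with it the placebo slope rests on four subjects. That is a trade-off, not a clear fault.

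Adjusting for condition also does not settle everything. At session 2 the MDMA arm receives 100 mg or 125 mg according to group, so dose could still drive both variables within that arm. The 5% rate after adjustment assumes that it does not.

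**Conclusion.** The point holds in conditional form. SAP 8.10.3 leaves out arm for the one sample where arm is expected to matter most, and the method as written cannot support the surrogate and mechanism aims. If MDMA shifts the second-session biomarker by 2 to 3 SD and LSAS by 1 to 1.5 SD, with no within-arm link, the expected pooled r is -0.29 to -0.47. A nominal 5% test then rejects in about 16% to 40% of trials. With shifts of 1 SD in both, it rejects in about 9%. These shifts are assumptions, since the documents give none. This is a point about how an exploratory result could be misread. It does not threaten the primary analysis.

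**What to change.** In SAP 8.10.3:
- Replace the unqualified correlation with a partial correlation, or a regression of the LSAS outcome on the biomarker level, adjusted for Stage 1 condition. State which LSAS assessment is used with each sample.
- Report the estimate with its confidence interval, and show scatter plots marked by arm and by dose received.
- Describe any sample taken at or after the LSAS assessment it is related to as association and not prediction. This certainly applies to the six-month sample against visit 13.
- Reconcile the two-week and one-month times given for the post-session sample across the protocol and SAP.

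The change is to wording only and needs no new data. It costs one degree of freedom, and the adjusted analysis has little power at N = 12, so it should be presented as an estimate. Dose differences within the MDMA arm remain unadjusted; marking dose on the plots lets a reader see them but does not remove them.

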8.10.3.1 Process Measures

Belief of Treatment Group Assignment

In order to compare the therapists’, independent raters’, and subjects’ belief of treatment group to actual dose received in each blinded session, the number and frequency of correct guesses will be calculated and depicted by treatment group and study role (subject, therapist, or independent rater).

Feedback Questionnaire

The Feedback Questionnaire nominal variables will be described in terms of frequencies and percentages, while ordinal and non-normal continuous variables will be described using sample mean, standard deviations, and range.

8.10.4 Safety Analyses

The primary measure of safety will be the reporting of adverse events. The Adverse events considered are Treatment Emergent Adverse Events (TEAE) defined as those AE's that occurred after dosing and those existing AEs that worsened during the study. Verbatim terms on case report forms will be mapped to preferred terms and system organ classes using the MedDRA dictionary. For incidence reporting if a subject has more than one adverse event mapped to the same preferred term, that adverse event will be reported only once using the highest severity and closest relationship to study drug. Subject incidence of adverse events will be displayed by Stage I treatment group and by system organ class. Adverse events will also be summarized by severity and relationship to study drug. Subject incidence of serious adverse events by Stage I treatment group will also be displayed. In addition to the listing of all adverse events, a listing of serious adverse events and a listing of adverse events leading to discontinuation of study drug will be included.

Summary tables of frequency listings of expected adverse events (Spontaneously Reported Reactions) mapped to preferred terms will be displayed during and after each experimental session by Stage I treatment group.

Columbia Suicide Severity Rating Scale (C-SSRS)

Suicidal ideation and behavior will be summarized according to suggestions made in the Columbia-Suicide Severity Rating Scale Scoring and Data Analysis Guide [3]. A positive response for suicidal ideation is counted when a subject answers "yes" to any one of the five suicidal ideation questions (Categories 1-5) on the C-SSRS, i.e. a score > 0 for suicidal ideation score. Serious suicidal ideation is a suicidal ideation score of 4 or 5. A positive response for suicidal behavior occurs when a subject answers "yes" to any one of the five suicidal behavior questions (Categories 6-10) on the C-SSRS, i.e. a score > 0 for suicidal behavior score. The number and percent of positive responses of Positive Ideation, Serious Ideation, and Positive Behavior will be tabulated by Stage I treatment group and time period. Compare lifetime serious suicidal ideation and positive behavior frequencies to cumulative frequencies anytime during the study until end of stage 1 and stage 2.

Subjective Units of Distress (SUD)

Descriptive statistics for SUD scores will be calculated by Stage I treatment group and time period with counts and percentages.

Vital signs

Vital signs (heart rate, body temperature, systolic and diastolic blood pressure) will be summarized using descriptive statistics at baseline and at each post-baseline time point. Occurrences of systolic and diastolic blood pressure, heart rate, and body temperature readings above the pre-determined cutoff will be displayed with numbers and percentages by timepoint.

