3.2 Secondary Objectives

The following objectives will compare MDMA and placebo groups in the blinded Stage 1:

- To assess effects on levels of oxytocin (OT), arginine vasopressin (AVP), and cortisol (CORT) in peripheral blood at baseline, once during each experimental session between hours 2 – 3, one month after the second experimental session, and at 6-month follow-up.
- To assess effects on social perception using The Awareness of Social Inference Test (TASIT) at baseline, once during each experimental session between hours 2-3, one month after the second experimental session, and at 6-month follow-up.

- To assess effects on emotion labeling using the Toronto Alexithymia Scale-20 (TAS-20) at baseline, one month after each experimental session, and 6-month follow-up.
- To assess effects on emotion regulation using the Emotion Regulation Questionnaire (ERQ) at baseline, one month after each experimental session, and 6-month follow-up.
- To assess effects on depression symptoms as measured by the Beck Depression Inventory-II (BDI-II) at baseline, one day, two weeks, one month after each experimental session, monthly by mail during the 5 months leading up to the 6-month follow-up assessment.
- To assess effects on perceptions of stress as measured by the Perceived Stress Scale (PSS) at baseline, within 24 hours after each experimental session, one month after each experimental session and monthly by mail leading up to the 6-month follow-up assessment.
- To assess effects on four aspects of empathy, as measured by the Interpersonal Reactivity Index (IRI) at baseline, within 24 hours after each experimental session, one month after each experimental session, and at the 6-month follow-up assessment.
- To assess effects on self-esteem as measured by the Rosenberg Self-Esteem Scale (RSES) at baseline, within 24 hours after each experimental session, one month after each experimental session, and at the 6-month follow-up assessment.
- To assess effects on state and trait anxiety as measured by the State-Trait Anxiety Index (STAI Form Y) at baseline, one day, two weeks, and one month after each experimental session, and monthly by mail leading up to the 6-month followup assessment.

The following objectives will compare effects in specified subjects:

- To determine if subjects who receive placebo in Stage 1 show a reduction in LSAS scores after two open-label sessions in the Stage 2 crossover

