3.3 Safety Objectives

The safety objectives of the study are to monitor and assure safety of subjects during and after the experimental sessions by assessing physiological effects, psychological distress, adverse events, spontaneously reported reactions and suicidality.

- Vital signs (BP, HR, BT) will be measured at baseline and every hour during experimental sessions until they return to baseline.
- Participant distress will be measured by the Subjective Units of Distress (SUD) scale at baseline and every hour during experimental sessions until return to baseline.
- Risk of suicide will be measured by the Columbia Suicide Severity Rating Scale (C-SSRS) during all in person visits, as well as twice during each experimental session at two hours after drug administration and the end of the experimental session, and on Day 2 and Day 7 after each experimental session.
- SAEs and AEs will be assessed throughout the study and spontaneously reported reactions, defined as expected AEs, will be assessed during each experimental session and for seven days after each experimental session, or until resolution.
- In addition to spontaneously reported reactions, symptoms specific to the study population will be collected at baseline and tracked throughout the study

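### The SAP's adverse event and SAE incidence tables use the Stage 1 treatment group with no Stage 2 cut-off, so open-label MDMA events in crossed-over placebo subjects count under placebo

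*SAP*

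**What the plan says.** SAP 8.10.4 sets the adverse event table as follows: "Subject incidence of adverse events will be displayed by Stage I treatment group and by system organ class". For serious events: "Subject incidence of serious adverse events by Stage I treatment group will also be displayed". Treatment-emergent events are those that "occurred after dosing and those existing AEs that worsened during the study". If a subject has several events under one preferred term, "that adverse event will be reported only once using the highest severity and closest relationship to study drug". None of these sentences mentions Stage 2. The summaries by severity and by relationship to drug name neither a grouping nor a period. The Safety population (SAP 8.1) is everyone given any study treatment, again without a stage limit.

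Other displays in the same section do carry a period. Suicidality counts "will be tabulated by Stage I treatment group and time period", the distress scale is handled likewise, and expected reactions "will be displayed during and after each experimental session by Stage I treatment group".

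Stage 2 is open only to placebo subjects, who are offered two MDMA sessions (SAP 4.0; Protocol 5.2.8) with the same safety measures as in Stage 1. SAEs are collected through termination (Protocol 8.5), which for these subjects is the end of Stage 2. Neither document plans a separate Stage 2 adverse event table. The adverse event frequency tables in Protocol 12.0 have no stage rule either.

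**The concern.** The Stage 1 treatment group is a label that a subject keeps for the whole study. Using it as the column heading does not restrict which events are counted. A placebo subject who crosses over is still in the placebo column when MDMA is given, so the column mixes placebo and MDMA experience while the MDMA column does not change.

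Two consequences follow. The displayed MDMA-placebo contrast is pulled towards zero, and can change sign, as more subjects cross over. The worst-case rule adds to this: a more severe or more closely related Stage 2 event replaces a milder Stage 1 placebo event of the same term, so the placebo column can take on MDMA severity and relationship as well as MDMA counts.

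Protocol 12.0 describes this as primarily a safety study and says that safety data will help choose the dose for future studies. A misleading comparator column therefore bears on a main use of the trial.

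**Working it through.** **Exposure, from the dose regimen table (Protocol 2.4; SAP 4.0)**

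- Stage 1 MDMA sessions: 8 subjects × 2 = 16. Stage 1 placebo sessions: 4 × 2 = 8. Stage 2 MDMA sessions: at most 4 × 2 = 8.
- Total MDMA sessions: 16 + 8 = 24, which reproduces the maximum in Protocol 2.3.
- With full crossover, 8/24 = 33% of MDMA sessions fall under placebo, and 8/(8 + 8) = 50% of the placebo column's sessions are MDMA sessions.
- Planned MDMA per crossed-over placebo subject: 75 + 125 = 200 mg. MDMA-group mean: (4 × 175 + 4 × 225)/8 = 200 mg. Over the whole study the two columns have the same mean planned exposure per subject.
- Collection of all adverse events (Protocol 8.5: session day plus seven days) is at least 4 × 8 = 32 days for a crossed-over subject and 2 × 8 = 16 for an MDMA subject. These are minima, because events are also followed until they resolve. Planned participation is 10 against 8 months (Protocol 4.1).
- One open-label SAE would read as 1/4 = 25% on placebo.

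**Effect on the displayed difference**

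Let p0 and p1 be the Stage 1 subject incidences on placebo and MDMA, p2 the Stage 2 incidence, and k the number of the four placebo subjects who cross over. The documents give no rates, so all values are assumptions.

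Expected displayed difference = p1 − [(4 − k)p0 + k·c]/4, where

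- c = 1 − (1 − p0)(1 − p2) if a subject's events in the two stages are independent;
- c = max(p0, p2) if they are fully dependent.

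With k = 4 and p2 = p1 this becomes −p0(1 − p1) or 0. For example, with p0 = 0.25 and p1 = p2 = 0.75: c = 1 − 0.75 × 0.25 = 0.8125, and the difference is 0.75 − 0.8125 = −0.0625.

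Difference in percentage points, independence (full dependence):

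| p0 / p1 | Stage 2 risk | 0 of 4 cross | 2 of 4 | 4 of 4 |
|---|---|---|---|---|
| 25 / 75 | equal to p1 | +50 (+50) | +22 (+25) | −6 (0) |
| 25 / 75 | half of p1 | +50 (+50) | +36 (+44) | +22 (+38) |
| 10 / 30 | equal to p1 | +20 (+20) | +7 (+10) | −7 (0) |
| 10 / 30 | half of p1 | +20 (+20) | +13 (+18) | +7 (+15) |

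**Chance of a misleading table**

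Exact binomial calculation with 8 MDMA and 4 placebo subjects, all four crossing when there is no cut. Ranges run from full dependence to independence.

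| p0 / p1 | Outcome shown | Stage 1 cut | No cut, equal Stage 2 risk | No cut, half risk |
|---|---|---|---|---|
| 25 / 75 | MDMA no higher than placebo (ties included) | 6% | 61–71% | 14–30% |
| 25 / 75 | MDMA strictly lower | 2% | 43–53% | 7–17% |
| 10 / 30 | MDMA no higher than placebo (ties included) | 25% | 57–67% | 34–48% |
| 10 / 30 | MDMA strictly lower | 12% | 40–50% | 18–31% |

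If MDMA had no effect (p0 = p1 = p2 = p) and all four crossed, independence gives −p(1 − p): −9, −19 and −25 points at p = 10%, 25% and 50%. The table would then make placebo look worse than MDMA.

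**The case against.** The strongest reply is that a Stage 1-only display is probably what the authors meant. The comparative secondary objectives are confined to Stage 1 ("The following objectives will compare MDMA and placebo groups in the blinded Stage 1"), and elsewhere the SAP names Stage 2 when it wants Stage 2 data. SAP 8.11 times only the primary efficacy analysis, so it does not show that the safety tables will pool stages. The intention may well be so, but no sentence says it. The safety objectives have no such limit ("SAEs and AEs will be assessed throughout the study"), 8.10.4 itself uses Stage 2 data for the suicidality comparison, and the displays in that section that need a period name one. On timing, SAP 8.11 shows only that Stage 2 events will be in the data set by the primary analysis.

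A second reply is that the largest drug signal is shielded. Common expected reactions go on a separate form and are tabulated by session, moving to the adverse event form only if they last beyond seven days. This stands. The affected tables hold mainly other, persistent or medically attended events and SAEs, so a contrast as wide as 25% against 75% may not arise in them.

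Third, the numbers are assumed, crossover is optional, and the largest distortions need all four subjects to cross with Stage 2 risk equal to Stage 1 MDMA risk. This also stands, which is why partial crossover and half risk are shown. With so few subjects the tables are noisy even with the correct cut: 25% for ties or reversal at 10/30.

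Finally, the tables are descriptive, at most four subjects are involved, and full listings allow each event to be traced. These points limit the severity. They do not correct a column whose heading misstates the treatment received.

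**Conclusion.** The concern holds. As written, SAP 8.10.4 assigns open-label MDMA events to the placebo column of the adverse event and SAE incidence tables, and neither document supplies a rule that prevents it. The finding does not extend to expected reactions, suicidality or the distress scale, which are split by session or period.

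From the documents alone, up to 8 of 24 MDMA sessions are misattributed and a single open-label SAE becomes 25% on placebo. How far the contrast shrinks depends on crossover uptake, on the true rates and on how a subject's events in the two stages are related. Under the assumed rates it ranges from modest attenuation to a small reversal. It should be fixed before the tables are produced. It does not threaten the efficacy analysis, and no decision rule depends on these tables.

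**What to change.** Amend SAP 8.10.4:

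1. Limit the Stage 1 treatment-group tables for adverse events, SAEs, severity and relationship to events with onset or worsening from the first Stage 1 dose to completion of the 6-month follow-up visit (V14), or to the last Stage 1 contact if earlier.
2. Apply the once-per-preferred-term rule separately within each stage.
3. Show events from the first Stage 2 dose onward in a separate column for open-label MDMA in former placebo subjects. Its denominator should be placebo subjects given at least one Stage 2 dose. The Crossover population in SAP 8.1 is unsuitable because it requires completion of Stage 2 and would drop anyone who stopped after one dose. List events between V14 and the first Stage 2 dose separately, so that none is counted twice.
4. Where a partial date leaves the stage unclear, assign the stage from all recorded information, including the visit of collection. SAP 8.3 imputes an unknown month to the first dose date when the year matches, which could move a Stage 2 event into Stage 1.

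Items 1 to 3 are the core; item 4 and the interval listing close smaller gaps. The cost is a few sentences, one extra column in the four sets of tables and one short listing, with no new data.
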